11.2 Unanticipated Problems (UPs)

Per Stanford IRB, UPs are events involving risks to participants or others and must meet ALL 3 criteria below:

1. **Unexpected:** in terms of nature, severity, or frequency, given (a) the research procedures described in the protocol-related documents, and (b) the characteristics of the subject population being studied; AND
2. **Related to participation in the research:** or there is a reasonable possibility that the incident, experience, or outcome may have been caused by the procedures involved in the research; or if a device is involved, probably caused by, or associated with the device; AND
3. **Harmful:** suggests that the research places subjects or others at a greater risk of harm (including physical, psychological, economic, or social harm) than was previously known or recognized.

UPs generally will warrant consideration of substantive changes in the research protocol or informed consent process/document, or other corrective actions, in order to protect the safety, welfare, or rights of subjects or others. (27) Due to this, UPs will be reported promptly to Stanford IRB following the below guidelines.

A UP may also be an AE or SAE and can be noted as both on CRFs and in OnCore.

11.2.1 Reporting UPs

UPs should be entered into OnCore and reported [within 24 hours of learning of the event. Reporting can be done via email to Stanford Cancer Clinical Trials Office \(CCTO\) at \[[contact]\]\(mailto:[contact]\), copying [name] and Stanford research staff \(Research Nurse or Research Coordinators\), with subject line: "SECURE: PanCRS STUDY Unanticipated Problem."](#) A Case Report Form (CRF) describing the event must be supplied and can be sent as an attachment to the email. It could be generated from the OnCore entry (as a pdf or report), or using the Case Report Form in Appendix V.

Stanford research staff will notify Stanford IRB via 'eProtocol' as per regulatory guidelines. The UP may also be forwarded to other Stanford regulatory boards, e.g., DSMC, as applicable.

Any questions, issues, or need for clarification of the UP by Stanford IRB will go through Stanford study PIs or Coordinators to the participating center research staff.

Participating centers are responsible for reporting Unanticipated Problems or similar events to their IRB within their institutional timeframes and guidelines.

Participating sites should also:

- Place copies of the UP Report in the patient’s study chart and in the regulatory binder (electronic regulatory binder is allowed).
- Follow patient and provide update to Stanford until any of the below:
 - Resolution of event
 - Resolution of event with sequelae
 - Death of patient

SAE and UP Reporting Requirements				
Hospitalization	Grade 1	Grade 2	Grade 3	Grade 4/5
Hospitalization ≤ 24 hrs	UP's within 24 hours	UP's within 24 hours	Report SAE and UP within 24 hours	Report SAE and UP within 24 hours
Hospitalization ≥ 24 hrs	UP's within 24 hours	UP's within 24 hours	Report SAE and UP within 24 hours	Report SAE and UP within 24 hours

SAE Definition: Fatal, life threatening, requires hospitalization or prolongs hospitalization, results in persistent or significant disability, causes congenital anomaly/birth defect or significant medical event.
				

Unexpected Problem (UP) Definition: Unexpected in terms of nature, severity, or frequency. Related to participation in the research. And Harmful suggesting that the research places subjects or others at a greater risk of harm.
				

To report all UP's and SAEs Grade 3 and above: 1)Enter the event into OnCore, 2)send email to [name] and Stanford research staff ([name]) with the subject line: "SECURE: PanCRS STUDY Serious Adverse Event" and 3)Include Case Report Form describing the event and submit follow up reports for the resolution of the event. For any questions regarding whether an event is an SAE or a UP, please email [name] and [name].
				

[name]: [contact] [name]: [contact]
				

11.3 Adverse Events (AEs) and AE Monitoring

An AE is defined as any untoward medical occurrence in a clinical investigation subject, regardless of causal attribution.

All AEs should be graded according to the NCI Common Terminology Criteria for Adverse Events, Version 4.0, available at <http://ctep.cancer.gov/reporting/ctc.html>.

AEs should be:

- Assessed at each consultation or follow-up visit,
- Assessed during each mFFX cycle (prior to infusion is acceptable), and
- Recorded on the AE Tracking form in Appendix V.

Laboratory tests (CBC with differential and CMP) should also be obtained with each mFFX administration, and abnormal values also noted on the AE Tracking Form indicating AE Grade if applicable.

AEs should also be:

- Reported to Stanford as per protocol guideline and upon request
- Noted in patient study charts and binder
- Entered into REDCap CRFs
- Reported to the participating center's IRB as per their institutional guidelines.

AEs in REDCap CRF should remain current and may be requested by Stanford for study renewals, audits, reports, analyses or other submissions for Stanford IRB, SRC, or DSMC. AEs may also be reviewed by members of the study monitoring group in meetings, audits, and/or site visits.

Updates and outcomes of AEs, SAEs, UPs, and deviations may take place during teleconferences or more frequently as needed.

11.4 Deviations

A protocol deviation is any unapproved discrepancy from a protocol research plan or Good Clinical Practice (GCP) guidelines, except where necessary to eliminate an immediate hazard to trial subjects.

11.4.1 Documenting and Reporting Deviations

Serious or Major Deviations

Research staff should promptly report serious or major deviations, or those that affect participant eligibility, informed consent, or protocol endpoints; and/or any deviation that could potentially result in harm to participants. These should be reported within 24 hours of the deviation or of learning of the deviation, by entering them into OnCore. The OnCore record should include the following:

- description of the deviation,
- corrective action taken,
- a statement whether the patient was harmed or could have been potentially harmed by the deviation, and

- whether the deviation was reported to the participating center’s IRB, and/or Stanford IRB.

Stanford research staff should also be immediately notified of the deviation, [via email to](#) [name], copying the study Research Nurse or Research Coordinator with subject line: “SECURE: PanCRS STUDY Major Deviation.” A Case Report Form (CRF) describing the event is required and could be generated from the OnCore entry (as a pdf or report) and attached to the email.

Stanford DSMC reviews deviations in OnCore to ensure completeness of the deviation report and ensure the safety of trial participants. The DSMC may request corrective action and/or prompt reporting to Stanford IRB. If reporting to Stanford IRB is required, Stanford’s research staff (Study Nurse or Coordinator) will assist with this by entering the deviation in ‘eProtocol’.

Any questions, issues, or need for clarification of the event by Stanford IRB will go through Stanford study PIs or Coordinators to the participating center research staff.

Participating sites should also:

- Place copies of the Deviation Report or CRF in the patient’s study chart and in the regulatory binder (electronic regulatory binder is allowed).
- Follow patient and provide update to Stanford until any of the below:
 - Resolution of event
 - Resolution of event with sequelae
 - Death of patient

Participating centers are responsible for reporting deviations to their IRB within their institutional timeframes and guidelines.

Minor Deviations

Deviations not meeting the above criteria for major or ‘serious,’ or that do not have a significant effect on the subject’s rights, safety, or welfare, or on the integrity of the data -- e.g., conducting a protocol-required visit out of the protocol ‘window’ -- should be documented on the Deviation Log in Appendix V.

Deviations in OnCore or in Deviation logs should remain current at all time, and may be requested by Stanford for study renewals, audits, reports, analyses or other submissions for Stanford IRB, SRC, or DSMC.

11.5 Study and Subject Reviews

Teleconferences will be held every other month for purposes of study and subject reviews, issues, and updates. Participating centers will have at least 1 research

team member partake and any pertinent study information will be communicated to PIs by the attending research team member(s). Any issues with patient compliance, database entry, toxicities, AEs, UPs, or SAEs, protocol updates or reviews, or other items will be discussed in calls.

Also, at times of study renewal and safety or interim analyses, research staff for each participating center will compile and submit requested patient data and clinical trial efficacy endpoints. These and other pertinent study data will be discussed and reviewed by the monitoring group to confirm whether outcomes favor continuation of the study.

Teleconferences will be coordinated by Stanford Research staff and any resultant reports will be distributed to participating centers' PI or assigned research team member.

12. CORRELATIVE/SPECIAL STUDIES

12.1 Laboratory Correlative Studies

12.1.1 Analysis of patient plasma for biomarker development

12.1.1.1 Collection of Specimen(s) (optional):

Collaborating centers who partake in this part of the study can have patients elect to participate in this portion of the study on the consent form.

Blood Samples

a) Blood (EDTA preserved) for research purposes may be drawn after re-staging scans when patient is enrolled and registered on-study, and then at each follow-up along with the patient's clinical labs. For each collection, up to 20ml (2 large lavender tubes at 10ml each) will be drawn.

b) Immediately after collection, blood will be centrifuged at 3000 RPM for 10 minutes and plasma collected. The supernatant will be aliquoted for storage at -80°C into separate tubes. The pellet will also be stored in a separate tube at -80°C.

12.1.1.2 Shipping of Specimen(s)

Samples may be shipped to Stanford for analysis. Samples will be shipped overnight by federal express on dry ice and sent in batches.

12.1.1.3 Site(s) Performing Correlative Studies

All biomarker studies will be performed at Stanford by [name] or in the laboratory of a research collaborator.

We will utilize proximity ligation assay (PLA) to simultaneously interrogate a panel of 60-100 secreted proteins that we have developed for pancreatic cancer patients. PLA is an antibody-based method of detection in which complementary single-stranded oligonucleotides are linked to each antibody pair. When the 2 antibodies bind in close enough proximity, the local concentration increases, allowing for PCR amplification of this signal. PLA is more sensitive than conventional ELISA and can be reliably multi-plexed for the detection of multiple protein panels (Fredriksson et al). In a pilot study, we have shown that when using this method of detection (Chang et al), we can accurately identify patients with pancreatic cancer. In this study, we will expand the number of biomarkers and collect plasma at multiple time points during therapy. The goal is to identify a biomarker panel that is predictive of patient outcome and/or response to therapy. We hypothesize that not only is the pattern of secreted biomarkers important but the change in these biomarkers may be even more critical for prediction of clinical outcomes.

12.1.1.4 Coding of specimens for privacy protection

At the time of enrollment each patient will be given a specific confidential identification number (IDN). Specimens will be stored under the patient's IDN. The information can be shared with other investigators listed on this protocol. Study data will be maintained in password protected computer files (protected online database through Johns Hopkins). Only research personnel will have access to this information.

12.2 Collection of Pre- and Post- Treatment Scans, Treatment Planning Scans, and Treatment Plans

12.2.1 Data and Image Collection

12.2.1.1 All images (CT, PET, or MR) including re-staging scans, treatment planning scans and follow-up scans will be transferred electronically to a secured database or on password-protected discs or encrypted drives, using an IDN assigned at registration for each patient. Specific parameters will be prospectively collected such as treatment volume and dose to adjacent structures.

The JHU database is set up to store ROI geometries and dose distributions along with the CT. This design facilitates the investigation of dosimetric effects on tumor response and complication utilizing DVH or other attributes of the 3D dose. For Pinnacle, the data can be directly placed in the JHU database via scripts. For other planning systems, DICOM RT data transfer will be used.

13. INVESTIGATOR RESOURCES

13.1 Qualifications

The study staff will include, but is not limited to, the Principal Investigator, Co-Investigators, research coordinators, research nurses, and any residents or fellows working with the study physicians at each institution. Also, laboratory personnel in the Principal Investigator's laboratory will be involved in analyzing the plasma and tumor specimens collected from patients.

All study staff will have completed the required training specific for their responsibilities in this study. Furthermore, each member of the research team from each institution will be given a thorough explanation of the protocol and their responsibilities. All research investigators will be required to complete proper training through their facility and institutional review boards.

13.2 Use of Cancer Center Facilities

Patients will be evaluated and treated in their respective institutions. All radiotherapy for this study will be performed in the department of radiation oncology at the participating institution. Other procedures related to this study (i.e., blood draws, tissue biopsy, imaging studies) will be carried out at each institution.

13.3 Conflict of interest

There is no potential conflict of interest among the research personnel involved in this study.

14. STUDY CALENDAR

Activity	Induction Chemotherapy				Study Treatment	Follow-up (Time From Completion of Study Treatment) ^j							
	Screening	Study Enrollment	Induction Chemo / mFFX ^g	Re-staging ^c		SBRT ^d	mFFX 2 cycles ^f	4-8 wks ^k	3 ^j mos	6 ^j mos	9 ^j mos	12 ^j mos	Yr 2-Q 6 ^j mos
Biopsy	X				R								
Negative Pregnancy test ^a	X				A								
Consultation	X	X	X ^g		N			X ^k	X	X	X	X	X
ECOG PS	X	X			D			X ^k	X	X	X	X	X
Labs: CBCD, CMP, CA19-9 (CEA optional)	X	X ^b	X ^g		O		X ^h	X ^k	X	X	X	X	X
Study/research labs ⁱ (optional)		X ⁱ			M		X ⁱ	X ^k	X ⁱ	X ⁱ	X ⁱ	X ⁱ	X ⁱ
Eligibility		X			I								
Informed Consent		X			Z								
Study Registration		X			E								
QOL		X						X ^k	X	X	X	X	X
Scan: CT or MR	X			X ^c				X ^k	X	X	X	X	X
PET/CT ^e	X ^e								X ^e				
AE evaluation						X	X ^h	X ^k	X	X	X	X	X
Seed placement						X							
Meds: PPI and pain meds ^j								X ^k	X	X	X	X	X
Sim/setup scans						X							
SBRT						X ^d							
Maintenance mFOLFIRINOX ^{fh}								X-----X ^{fh}					

^a Pregnancy test by urine or serum, for women who are not post-menopausal as defined in Appendix III.

^b Labs should be done within 30 days of eligibility confirmation.

^c Re-staging scan should be done within 2 weeks following completion of induction mFOLFIRINOX cycles.

^d SBRT should begin within 4 weeks of simulation and 8 weeks of the last chemotherapy; dose is 40 Gy (8Gy in 5 fractions).

^e PET-CTs are recommended but not required; if only 1 follow-up PET-CT is possible, recommendation is at 3 months.

^f mFOLFIRINOX should resume within 8 weeks after study treatment, and any breaks between chemotherapy cycles should not exceed 8 weeks. Patients may continue on maintenance mFFX as tolerated or per clinical judgment of treating physician.

^g Induction chemo/mFFX prior to enrollment is allowed through the 4th cycle of mFFX. No more than 4 cycles are allowed prior to randomization. The re-staging scan could be done within 2 weeks of completion of the chemotherapy cycle; records from labs and clinic visits are not required; mFFX infusion records should be collected.

^h Labs during mFFX cycles are as per institutional standard or treating Medical Oncologist. AEs should be assessed with each cycle of mFFX.

ⁱ Study labs are optional and for research purposes as explained in Section 12. Correlative/Special Studies; and may be drawn if patient agrees to this in the consent form.

- j Follow-up appointments 1 month before or after will be permitted, e.g. for 6-month follow-up, visit, labs, scan and QOL surveys can be done at 5-7 months.
- k 4-6 week follow-up visit and corresponding activities are *optional* and may be added if clinically indicated.

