7.2 Follow-up

All patients will be monitored with clinic visits, labs, and serial imaging (CT or MR scans and PET/CT if possible), and other tests as needed.

Patients deemed resectable at any time during follow-up may proceed to surgery. These patients will be withdrawn from the protocol and followed for survival.

Patients will have consultations in the first year every three months following study treatment as defined in the Study Calendar (Section 14); a follow up at 4-6 weeks is optional and may be done to assess subject's resectability, or if clinically indicated by study PIs or patient's treating physician.

For years 2 and 3, follow-up is recommended every 6 months, or until death or study withdrawal (due to progression, patient withdrawal, or noncompliance as defined in Section 7.5 Criteria for Removal from Study). Follow up intervals may be more frequent as indicated clinically. In the event of intolerable toxicity from mFFX, subjects will still be followed per protocol although chemotherapy may be altered or discontinued, the decisions of which will be left to the treating Medical Oncologist. Visits should include:

- Consultation with physical examination
- Labs: CBC, CMP, CA199. CEA and research bloods are optional.
- Scans: CT or MR and PET/CT if possible (PET/CT is recommended at 3 month follow-up visit but is not required)
- QOL (Quality of Life) Assessment with EORTC QLQ C-30 / PAN26 survey
- Adverse Event (AE) evaluation
- Concomitant Medications: PPIs and pain medications as applicable
- Other tests as appropriate.

Patients who remain on-study will be followed until death and cause of death should be obtained when possible.

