7.5 Criteria for Removal from Study

Patients will be withdrawn from the study for any of the following reasons:

- disease progression (as defined in Section 15.1.2 Disease Parameters)
- patient withdrawal
- pregnancy
- patient noncompliance, or failure of the patient to follow instructions of the study staff
- protocol director decides that continuing participation could be harmful to the patient
- treatment needed for patient that is not allowed in the study
- patient is deemed resectable and proceeds to surgery
- study cancellation
- other administrative reasons
- unanticipated circumstances.

Patients will continue mFFX on-study until one of these endpoints; in the event of intolerable toxicity from mFFX, subjects will still be followed per protocol although chemotherapy may be altered or discontinued, the decisions of which will be left to the treating Medical Oncologist.

Patients withdrawn from the study will be followed for overall survival only.

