15.1.5 Progression-Free Survival (or other time-to-event parameters)

The criteria for time to progression and progression-free survival (PFS) will be the time from randomization to documented progression or death. Individuals will be censored at the date of last evaluation for progression if neither event is observed. Overall survival will be defined as time from randomization until death from any cause. Participants will be censored at the date of last contact if the date of death is not observed. Local PFS will be the duration from randomization to local progression or death if death occurs before local progression. Metastasis free survival will be the duration from randomization to metastasis or death from any cause, if death occurs before metastasis. Individuals will be censored at the time of the last evaluation for local or distant progression, respectively, if neither progression nor death is observed.

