17.2 Analysis Populations

Efficacy analysis will be conducted on the intent-to-treat population which includes all randomized patients and on the per-protocol population. The per-protocol population will include patients who have completed 6 or more cycles of mFolfinirox treatment +/- SBRT.

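### PFS is timed from randomization but scans from completion of study treatment, which is not consistently defined by arm, so scan times can differ between arms and shift the Cox hazard ratio

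*Combined protocol and SAP*

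**What the plan says.** **Endpoint clock.** Section 15.1.5: "progression-free survival (PFS) will be the time from randomization to documented progression or death". Section 17.3.2 uses the same origin.

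**Scan clock.** The calendar's follow-up columns are headed "Follow-up (Time From Completion of Study Treatment", with CT or MR at 3, 6, 9 and 12 months and then every 6 months. Section 7.2 agrees: "Patients will have consultations in the first year every three months following study treatment as defined in the Study Calendar". Footnote j adds "Follow-up appointments 1 month before or after will be permitted". Footnote k says the "4-6 week follow-up visit and corresponding activities are" optional, so the only earlier scan may not happen.

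**What completion means.** No sentence defines it for each arm.
- The printed calendar places an SBRT column and a 2-cycle mFFX column before follow-up. Section 17.2 defines per-protocol patients as those who "completed 6 or more cycles of mFolfinirox treatment +/- SBRT", which fits 4 induction cycles plus 2.
- Footnote f says "mFOLFIRINOX should resume within 8 weeks after study treatment", which makes study treatment SBRT alone and gives the control arm no anchor.
- Section 7.5 says "Patients will continue mFFX on-study until one of these endpoints", and progression is one of those endpoints.

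**Intervals.** Section 6.2 recommends 2-4 weeks on each side of SBRT. Up to 8 weeks is permitted before it (5.3) and after it (7.1), and delivery may take up to 2 weeks (6.2). Control patients can go straight on with mFFX, with breaks of up to 8 weeks (5.3).

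**Analysis.** Section 17.4 compares arms by Cox model. Section 17.5.2 stops the trial for efficacy on the confidence interval for the hazard ratio. Neither deals with assessment timing.

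**The concern.** An imaging progression is dated by the scan that finds it. If one arm's scans fall later after randomization, its progressions are recorded later even when the disease behaves identically, and the hazard ratio moves away from 1 with no treatment effect.

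The plan allows this in two ways. The SBRT arm alone contains the SBRT step and its two intervals, so any clock that starts after that treatment starts at a different point from the control clock. And because completion is not consistently defined, sites may choose different anchors for control patients, so even the direction of the shift is open. At stake are the two-sided 5% error rate claimed in 17.3.2 and the interim efficacy rule. Overall survival is unaffected.

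**Working it through.** **1. The plan's own figures reproduce.** With exponential PFS, λ = ln 2 / median, accrual A = 60 and minimum follow-up F = 12 months, the event probability per arm is 1 − [exp(−λF) − exp(−λ(A+F))]/(λA).
- Control, median 6: 86 × 0.964 = 82.9 events.
- SBRT, median 10.2: 86 × 0.893 = 76.8 events.
- Total 159.7 (plan: 83 + 77 = 160).
- Schoenfeld power: HR = 6/10.2 = 0.588, and Φ(0.531 × √160/2 − 1.96) = 91.9%. Freedman gives 90.6% (plan: 91%).
- Events at 36 months: 71.7 (plan: 71).

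The sample size is not in dispute.

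**2. Where the scan clock starts, in weeks after randomization.** Recommended gaps are 2-4 weeks each. I assume 1 week of SBRT delivery and 1-3 weeks used up before randomization by restaging, report submission and assignment. Two cycles take 4 weeks.

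Reading A (completion = SBRT plus 2 cycles):
- SBRT arm: max(gap1 − used, 0) + 1 + gap2 + 4. Range 0+1+2+4 = 7 to 3+1+4+4 = 12; mean about 9.
- Control: 4 without breaks.
- Lag: 3 to 8 weeks, mean 5.0. With assumed control breaks of 0-4 weeks, mean 3.0.

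Reading B (completion = SBRT alone):
- SBRT arm: max(gap1 − used, 0) + 1, mean about 2.
- Lag: +2.0 weeks if sites anchor control at randomization, −2.0 if at the end of 2 cycles, −4.0 if that end is delayed by breaks.

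Under reading A without breaks, the month-3 scan falls on average about 3.9 months after randomization in control (3 + 4/4.35) and 5.1 months in the SBRT arm (3 + 9/4.35).

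**3. Null simulation.** Both true medians are 6 months, with 86 per arm, uniform accrual over 60 months and 12 more months of follow-up. Scans fall at 3, 6, 9, 12, 18, 24, 30 and 36 months after the anchor, each moved uniformly by up to 1 month. Progression is dated at the next scan, except that 0, 30 or 50% of events are dated exactly (deaths, clinical progression). Censoring is at the last scan. Cox tests are at month 36 (two-sided 0.00305) and month 72 (two-sided 0.05), with 20,000 replicates (standard error about 0.15-0.2 point on final rates).

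Final analysis, no optional scan. Each cell gives the HR, then % significant favouring SBRT / favouring control (nominal 2.5/2.5):

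| Anchors | 0% exact | 30% exact | 50% exact |
|---|---|---|---|
| A | 0.903, 9.4/0.5 | 0.940, 6.3/1.0 | 0.962, 4.5/1.5 |
| A, control breaks | 0.920, 7.6/0.6 | 0.954, 4.6/1.2 | 0.971, 3.8/1.6 |
| B, control at randomization | 0.951, 5.1/1.3 | 0.972, 3.8/1.6 | 0.983, 3.5/2.1 |
| B, control at end of 2 cycles | 1.053, 1.1/5.2 | 1.030, 1.7/3.7 | 1.017, 1.9/3.1 |
| Same, control breaks | 1.083, 0.7/7.2 | 1.050, 1.3/4.9 | 1.028, 1.7/3.9 |
| Both arms from randomization | 0.998, 2.5/2.4 | 0.999, 2.7/2.4 | 0.998, 2.8/2.6 |

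With the optional 4-6 week scan done in half of patients in both arms, at 0/30/50% exact dating:
- Reading A: HR 0.933/0.958/0.976, with 6.5/4.6/3.5% favouring SBRT.
- Reading A with control breaks: HR 0.945/0.967/0.980, with 5.5/3.9/3.5% favouring SBRT.

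Under reading A the interim boundary is crossed in favour of SBRT in 0.2-0.7% of trials (nominal 0.15%). Mean differences in median PFS are at most 0.10 month. One-year PFS in reading A moves the other way, by −2.9 to −0.7 points (SBRT minus control).

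**4. Outer bound.** Put every SBRT patient at every permitted limit (8 + 2 + 8 weeks, 2 of them used before randomization, plus 2 cycles), with no control breaks. Reading A then gives HR 0.84/0.88/0.92 and 19.1/12.0/8.3% favouring SBRT at 0/30/50% exact (6,000 trials, log-rank test). This is a limit, not an expectation.

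**The case against.** - **The anchor may be clearer than it looks.** The calendar has a separate row for maintenance mFFX running through follow-up, so 7.5 can be read as describing maintenance. Footnote f may be loose wording, since 7.1 states the same 8-week rule from completion of SBRT. The calendar was flattened from PDF, so the span of its headings is uncertain. This is fair: 7.5 alone is not a firm contradiction, and reading A is the more natural one. But footnote f still conflicts with the printed columns, and reading A is the reading with the larger bias towards SBRT.
- **No exact dating is the least plausible setting.** PFS counts deaths, 7.4 allows clinical progression, and 7.2 allows more frequent follow-up. That stands, and the 30-50% columns deserve more weight. At 70% exact the HR is 0.98-1.01 across anchors, with two-sided error 5.0-6.0% (4,000 replicates). The documents give no share.
- **The stated objective is median PFS, which hardly moves.** True at the recommended intervals. But 17.4 compares the arms by Cox model and 17.5.2 uses the hazard ratio, and that is where the shift appears.
- **The direction is indeterminate.** Also true. It limits any claim of bias towards SBRT, but an anchor that can push the result either way is itself a defect.

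**Conclusion.** The concern holds. The plan uses different clocks for endpoint and scans, does not define the scan clock consistently by arm, and has no analysis that corrects for the difference.

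At the recommended intervals the effect is modest. Over all reading A runs, with and without the optional scan, the null hazard ratio is 0.90-0.98 and two-sided error 5.2-9.9%. With 30-50% of events dated exactly and no optional scan, these are 0.94-0.97 and 5.4-7.3%. Reading B gives 0.95-0.99 (5.1-6.4%) with control anchored at randomization, or 1.01-1.08 (5.1-7.9%) with control anchored at the end of 2 cycles.

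The weeks used before randomization, control breaks, share of events dated exactly and uptake of the optional scan are assumptions. The documents give none of them, so size and direction carry only medium confidence. The defect should be fixed because the remedy is cheap; it does not undermine the sample size or overall survival.

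**What to change.** 1. In 7.2 and the calendar, schedule tumour imaging in both arms at identical times from randomization, whatever the treatment delays: for example months 3, 6, 9 and 12, then every 6 months, keeping the 1-month window. In the simulation this returns the hazard ratio to 1.00 and two-sided error to 5.0-5.4%.
2. Reconcile the calendar columns, footnote f, 7.5 and 17.2, so that study treatment and its completion have one definition per arm for any visit that stays anchored to treatment. This step alone would not equalize scan times.
3. Add to 17.4 an interval-censored PFS sensitivity analysis using actual scan dates.

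The cost is wording plus one sensitivity analysis, with the same number of scans. Scans, labs, QOL and AE checks now share one visit schedule, so sites may have to run two. Some SBRT-arm scans would fall sooner after SBRT. At the permitted limits (8 + 2 + 8 = 18 weeks, less 1-3 used, so 15-17 weeks after randomization) a month-3 scan could precede the restart of mFFX.
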